#### 6.4.2 Withdrawal of Individual Subjects

Parent/legal guardian of the subject can request to end the study at any time and for any reason if they wish to do so without any consequences or loss of benefits to which they are otherwise entitled to. Subjects may be withdrawn from the study prior to completion for reasons such as safety concerns, failure to adhere to protocol requirements, withdrawal of consent, etc.

Any data collected until the time of subject withdrawal may not be included in the final data analysis.

Information on the subject's withdrawal will be clearly documented in the case report forms along with reason of the withdrawal and will be notified to the Sponsor, as well as providing documentation in the medical records.

6.4.3 Follow-up for subjects withdrawn from study

None. There are no long term effects anticipated from participating in this study.

6.4.4 Replacement of individual subjects after withdrawal

In case a subject leaves the study prematurely, another volunteer may be recruited.

[figure not shown]
#### 7 STUDY PROCEDURES

#### 7.1 Informed Consent and Screening Procedure

Following identification of a potential eligible subject as defined by the inclusion and exclusion criteria, the child's parent(s), guardian(s), legally authorized representative, and/or the subject (when age appropriate) will be approached by the study staff, who will explain the purpose and procedures of the study in respect to potential risks & benefits, and clarification of subjects rights & privacy information.

- 7.1.1 Once all their questions have been answered and the informed consent signed, they will be enrolled in the study. The Investigator shall retain a copy of the signed informed consent document in each subject's record and provide a copy to the subject. The Investigator shall not allow subjects to participate in the study or consent any subjects prior to receiving IRB approval of the informed consent form.
- 7.1.2 Subject's demographic information (including, but not limited to, age, weight, height, race, ethnicity, skin tone pigmentation via Massey Scale, fingertip diameter, etc.) and subject's medical history will be recorded on CRF.
- 7.1.3 The point of enrollment is defined as the time at which a patient has signed and dated the consent form.
- 7.1.4 Study exit is defined as when the subject has completed the noninvasive device readings.
- 7.2 Noninvasive readings:

- 7.2.1 Subject will be fitted with the FDA-cleared pulse oximeter sensor at respective finger or toe location per manufacturer's Directions for Use (DFU) for the sensor (refer to Investigator Brochure).
- 7.2.2 Subject will be fitted with the investigational INVSENSOR00004 sensor per manufacturer's DFU. The INVSENSOR0004 sensor may be placed at the following locations depending on the subject's accessibility:

- Neck region: either side of larynx or suprasternal notch
- Chest region: sub-clavicle tissue below collarbone
- 7.2.3 As an additional piece of information for the study, a photo of the INVSENSOR00004, while it is attached to the subject, may be taken by the study staff. The study staff will notify the subject and/or subject's parent/guardian prior to taking the photo. The photograph will be taken so that no facial features of the subject are captured to protect the subject's privacy and confidentiality.
- 7.2.4 The investigational INVSENSOR00004 sensor and pulse oximeter sensor will both be connected to the RAM Dual patient cable. The patient cable is connected into the Radical 7 pulse co-oximeter.
- 7.2.5 Research study staff will assess if the subject can tolerate the capnography mask or nose sensor prior to recording data. The capnography sensor is connected into the Capnostream capnography.
- 7.2.5.1 If the subject is not able to tolerate with the capnography sensor then the capnography data will not be recorded.
- 7.2.6 Data will be recorded using laptop with the
- 7.2.7 Periodic checks will be made to ensure subject's well-being and tolerance of the sensors, and to check that sensors are connected. Refer to Procedure Manual for data collection details.
- 7.2.8 Periodic checks are to be performed at a frequency that is determined to be suitable by the PI and designated study staff
- 7.2.9 A minimum of manual breath-counts with the duration of each count will be performed at the start and towards the end of data collection. All measurements will be recorded in the CRF.
- 7.2.9.1 Additional manual breath counts ( duration) may be obtained depending on the length of the data collection period.
- 7.2.10 The length of the noninvasive INVSENSOR00004 sensor and pulse oximeter sensor readings will be a minimum of
- 7.2.11 Once the subject completes data collection or if the subject withdraws early prior to study completion, the sensors will be removed and the skin will be inspected for signs of redness or irritation. Any skin irritations will be recorded in the CRF and/or adverse event (AE) form.

#### 8 STATISTICAL PLAN

8.1 Sample Size Determination

8.1.1 For equivalence study the sample size is given by  $N = \left(\frac{(z_{\alpha/2} + z_{\beta}) \cdot \sigma}{\delta}\right)^2$  where

 $z_{\alpha/2}$  is the standard normal distribution z-score with tail area  $\alpha/2$ 

 $z_{\beta}$  is the standard normal distribution z-score with tail area  $\beta$ 

 $\delta$  is the limit of equivalence

 $\sigma$  is the a-priori estimate of standard deviation (precision)

For Type I error rate or  $\alpha = 5\%$ ,  $z_{\alpha/2} = 1.96$ 

For Type II error rate or  $\beta = 20\%$  or power = 80%,  $z_{\beta} = 0.85$ 

 $\delta = 2.0 \text{ RPM}$ 

 $\sigma = 3.0 \text{ RPM}$ 

$$N = \left(\frac{(1.96+0.85)\cdot 3}{2}\right)^2 = 18$$

This study will use a minimum of 18 subjects with up to 100 subjects to account for possible events such as subject withdrawal, device deficiencies, and/or incomplete cases.

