#### 4.2 Study Outcome and Measurement

Evaluation on the comparison of RRa measurements will be reported as a bias of between the acoustic respiration rate (RRa) parameter and the manual annotation (RRref).

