#### 8.2 Statistical Methods

8.2.1 The reference (RRref) will be obtained by measuring respiration rate based on manual annotations of respiratory inspirations and expirations. Bias will be reported using the following equation and will be used for each site, subject, and for all data combined:

$$Bias = \frac{1}{n} \sum_{i=1}^{n} (RR_a - RR_{ref})$$

8.2.1.1 Optional analysis may be performed based on the available capnography data collected from subjects who could tolerate the device. The statistical formula for calculating bias for the capnography results will be similar to the above equation but with RRa replaced by respiratory rate from capnography (RRcap).

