#### 13.4 Protocol Amendments

Any changes made to the clinical investigational plan/study protocol will be documented by way of an amendment. Before submitting protocol amendment to the IRB for approval, the protocol amendment must be agreed upon and signed by both the Investigator and the Sponsor. The Investigator shall not make any changes to the protocol without Sponsor approval and documented approval from the IRB. Both PI and Sponsor will retain the IRB approval letter and approved protocol as confirmation that the protocol amendment was approved.

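### The equivalence sample size in Section 8.1.1 allows for failure at only one limit, so the minimum of 18 subjects does not give the stated 80% power

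*Combined protocol and SAP*

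**What the plan says.** Section 8.1.1 opens with "For equivalence study the sample size is given by" and then gives N = ((z_alpha/2 + z_beta) × sigma / delta)². It states that delta "is the limit of equivalence" and sets it at 2.0 RPM. Sigma, a prior estimate of the SD, is 3.0 RPM. Alpha is 5%, entered as 1.96, and beta is 20%, entered as 0.85 with tail area beta rather than beta/2. The result is N = 18.

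The section then commits to a range: "This study will use a minimum of 18 subjects with up to 100 subjects to account for possible events such as subject withdrawal". Device deficiencies and incomplete cases are the other reasons given for going above 18.

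On analysis, Section 4.2 says "Evaluation on the comparison of RRa measurements will be reported as a bias", and Section 8.2 says "Bias will be reported using the following equation and will be used for each site, subject, and for all data combined". Neither section gives a confidence interval, a comparison with ±2 RPM or an assumed true bias. Section 8.1.1 does not say whether sigma describes single readings or subject means.

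**The concern.** An equivalence claim can fail in two ways: the interval for the bias can cross the upper limit or the lower one. When the true bias is 0 the two failures are equally likely, so the 20% allowed for beta has to be shared between them. The term in the formula should then be z_(beta/2) = 1.28, not z_beta = 0.85. The plan's formula counts only one of the failures.

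The 80% power is the plan's only justification for a minimum of 18 subjects. If 18 does not deliver it on the plan's own limit and SD, a study that closes near its minimum has a materially larger chance of failing to show equivalence than the plan states, even for a sensor with no bias.

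**Working it through.** **Inputs (Section 8.1.1):** delta = 2.0 RPM, sigma = 3.0 RPM, z_alpha/2 = 1.96, z_beta = 0.85, N = 18.

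**Assumptions added here:** one difference (RRa minus reference) per subject, because N counts subjects, and a true bias of 0, because the plan gives none. The per-side level is not settled by Section 8.2, so both usual choices are shown: 1.96 (2.5% per side, 95% interval) and 1.645 (5% per side, 90% interval).

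**Step 1. The plan's own figure.** ((1.96 + 0.85) × 3 / 2)² = 17.77, rounded up to 18. It reproduces.

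**Step 2. What that 80% refers to.** At N = 18, SE = 3/√18 = 0.707 and delta/SE = 2.828. The power to clear one limit is Φ(2.828 − 1.96) = 0.807. This is the plan's 80%.

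**Step 3. Power to clear both limits.** With true bias 0, power = 2Φ(delta/SE − z) − 1.
- At 1.96: 2 × 0.807 − 1 = 0.615.
- At 1.645: 2Φ(1.183) − 1 = 0.763.

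A simulation of 400,000 studies with known SD gave 0.616 and 0.764. With the SD estimated from the data (t distribution, 17 degrees of freedom), power is 0.522 and 0.715.

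**Step 4. N for 80% power.** The two-limit formula is N = ((z_alpha + z_(beta/2)) × sigma / delta)², with alpha per side.
- 2.5% per side: ((1.96 + 1.2816) × 1.5)² = 23.64, so 24.
- 5% per side: ((1.645 + 1.2816) × 1.5)² = 19.27, so 20.

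The t-based calculation gives 26 (N = 25 reaches only 78.4%) and 21 (N = 20 reaches only 78.0%).

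| Level per side | Power at 18, normal | Power at 18, t | N for 80%, normal | N for 80%, t |
|---|---|---|---|---|
| 2.5% (1.96) | 61% | 52% | 24 | 26 |
| 5% (1.645) | 76% | 71% | 20 | 21 |

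**Step 5. Sensitivity (normal approximation, N = 18).**
- True bias of 0.5 RPM, an assumed value: power = Φ(1.5/0.707 − z) + Φ(2.5/0.707 − z) − 1, which is 51% at 1.96 and 65% at 1.645.
- SD at which 18 subjects would give 80%: 2 × √18 / (1.96 + 1.2816) = 2.62, or 2 × √18 / (1.645 + 1.2816) = 2.90. Both are below the plan's 3.0.

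**The case against.** Four points can be made for the plan.

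- **No equivalence test is specified.** Sections 4.2 and 8.2 report bias only, so the 61% and 76% are powers of a test the plan does not write down. That is true, and the figures are conditional on it. But a power statement needs a test, and Section 8.1.1 names equivalence and a limit of equivalence. If the aim was instead to detect a 2 RPM difference, the formula fits and the labels are wrong. Section 8.1.1 needs correcting on either reading.
- **Eighteen is a floor.** Up to 100 may be enrolled, and at 1.96 the normal-approximation power is 81% with 24 subjects and 91% with 30. This limits the practical harm. It does not support the stated 80%, because the range is offered as cover for losses and not as a power target. Section 6.4.2 allows data from withdrawn subjects to be left out, and Section 6.4.4 makes replacement optional, so a compliant study could end near 18.
- **Sigma is undefined.** If 3.0 is the SD of single readings, the SD of subject means could be smaller, and at about 2.62 or 2.90 the 18 would suffice. This stands as a reason to treat the exact percentages as conditional. The fault in the formula does not depend on it.
- **The gap may be small.** At 5% per side it is under 4 points and 2 subjects by the normal approximation. That is so, but the plan prints 1.96, where the gap is about 19 points and 6 subjects.

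The footnoted sample-size text was not available. The power follows from the plan's own limit, SD and N, so it is not needed.

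**Conclusion.** The concern holds. The multiplication is correct; the choice of formula is the error. Eighteen subjects give about 80% power against one limit, but for equivalence within ±2 RPM they fall short of 80% at either usual per-side level. The loss is largest at the critical value the plan prints.

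This rests on one difference per subject, a subject-level SD of 3.0 RPM and a true bias of 0. Any real bias lowers the power further; a smaller subject-level SD would raise it. The shortfall applies when the evaluable number is at or near the minimum, not to every enrolment up to 100. It should be fixed. Confidence is high that the formula is wrong for equivalence; the exact percentages depend on the assumptions above.

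**What to change.** In Section 8.1.1:
- Replace the formula with N = ((z_alpha + z_(beta/2)) × sigma / delta)², with alpha stated per side and true bias 0 stated as an assumption, or use the t-based calculation for two one-sided tests.
- State that sigma is the SD of subject-level mean differences.
- Either keep 18 and state its actual power at the chosen level, or state an evaluable minimum that gives 80%, using the table above. The t-based figures are preferable because the SD will be estimated.

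In Section 8.2, name the confidence interval for the overall bias that matches the chosen level (95% for 2.5% per side, 90% for 5% per side), computed with the subject as the unit, and say that it will be compared with ±2 RPM.

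The cost is a protocol amendment. Section 13.4 says "Any changes made to the clinical investigational plan/study protocol will be documented by way of an amendment" and requires agreement by the investigator and sponsor, followed by IRB approval. Either the stated power becomes less favourable, or the evaluable minimum rises by 3 (to 21) or by 8 (to 26). The ceiling of 100 and the study procedures stay as they are.

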#### 5 CLINICAL SITES

This is a multicenter study that may enroll up to 100 total subjects. The subjects enrolled in this study may be recruited from the following sites:

Site	Site Name and PI	Site Description
1	Children's Medical Center Dallas (CMCD)	Children's Hospital (Pediatric Anesthesiology)
	Dallas, TX	
2	Loma Linda University (LLU)	Department of Anesthesiology
	Loma Linda, CA	

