#### 6.4 Subject Recruitment and Screening

Following identification of a potential subject, the patient will be approached by either the principal investigator or a designated research study staff (co-investigator and/or study coordinator), who will explain the purpose and procedures of the study. If the patient expresses an interest in participating in the study, they will be asked to read the Informed Consent Form.

All subjects will have their medical history reviewed at the time of screening, after informed consent has been obtained, by either the PI or the study staff who is delegated for this task. Subjects will be evaluated based on the inclusion and exclusion criteria to determine eligibility to be enrolled into the study. If a subject is deemed ineligible after screening, the subject will not be enrolled in the study. If the subject meets all of the inclusion and none of the exclusion criteria, the subject will be enrolled into the study.

Information regarding the subject's demographics (including, but not limited to age, weight, race, ethnicity, comorbidities, medications, etc.), preexisting allergies, skin abnormalities and other preexisting diseases/conditions that may be relevant to the study will be recorded within the CRF.

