#### 11.4 Data Transfer and Storage

- 11.4.1 Training on CRF completion will be provided to study personnel prior to data collection.
- 11.4.2 Original CRFs will be stored in a secure location at site and scanned copies will be sent to sponsor.
- 11.4.3 Only authorized sponsor personnel will have access to study data and will move all data related contents and CRF scans to a secure FTP. Masimo Clinical Research will have access to the FTP transferred data.
- 11.4.4 CRFs will be checked for accuracy and completeness of data. If there are inconsistent or missing data points, a data query list will be generated and submitted to the PI or designee, who shall both follow GDP practices for data correction by striking through the old entry, adding in new entry with initial and date, and resend to Masimo the corrected CRF. Once all queries have been resolved, Masimo engineers are notified that data is ready for analysis. To ensure data integrity, Masimo engineers will only have read access to study data, therefore are unable to unintentionally tamper with the original data files.

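### Section 8.1 computes 18 subjects but allows any number from 18 to 100, for a reason that does not explain the cap and with no rule for when enrolment ends before it

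*Combined protocol and SAP*

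**What the plan says.** - Section 8.1 uses alpha 5%, power 80%, an equivalence limit of 2.0 RPM and an SD of 3.0 RPM, and arrives at 18. It then plans for "a minimum of 18 subjects with up to 100 subjects to account for possible events". The only reason given is "to account for possible events such as subject withdrawal, device deficiencies, and/or incomplete cases". No loss rate is stated.
- Section 5 repeats the cap as a permission: "This is a multicenter study that may enroll up to 100 total subjects".
- Section 6.4.4 makes replacement optional: after an early exit "another volunteer may be recruited". Section 6.4.2 allows data from withdrawn subjects to be left out of the final analysis.
- Section 8.2 reports the mean of RRa minus RRref by site, by subject and overall. It gives no test, confidence interval or acceptance limit.
- Section 11.5 assigns the analysis and the report to the sponsor. On timing, section 11.4 says: "Once all queries have been resolved, Masimo engineers are notified that data is ready for analysis". That step is not tied to the close of enrolment.

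The plan states no number of evaluable subjects, no rule for ending enrolment short of the cap, no interim plan and no bar on comparing RRa with RRref early. The blanked-out items in section 7.2 concern recording and breath counts, so they do not account for these gaps.

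**The concern.** A loss allowance turns a target number of usable subjects into a somewhat larger number to enrol. Here the upper figure is 5.6 times the lower (100/18), with no assumption linking the two. Each subject has one non-invasive recording: study exit comes when the readings are complete (section 7.1.4), and withdrawn subjects have no follow-up (section 6.4.3).

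Two things are at stake. First, if 18 counts enrolled and not usable subjects, losses would take the study below the size that its own calculation requires. Second, stopping at 18, 47 or 100 would all comply with the plan. A reader of the results could not tell a size fixed in advance from one chosen after the bias had been seen.

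**Working it through.** **Inputs.** From section 8.1: z(alpha/2) = 1.96, z(beta) = 0.85, delta = 2.0 RPM, sigma = 3.0 RPM, range 18 to 100. Assumed, because the plan is silent: the loss rates, the timing of any looks, and independent normal differences between subjects.

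**1. The plan's figure.** N = ((1.96 + 0.85) × 3 / 2)² = 4.215² = 17.77, rounded up to 18. Unrounded z values give 17.66, also 18. The figure reproduces.

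**2. The cap as a loss allowance.** Enrolled = 18 / (1 − loss), rounded up.

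| Assumed loss | Enrolled to keep 18 |
|---|---|
| 10% | 20 |
| 20% | 23 |
| 30% | 26 |
| 50% | 36 |
| 82% | 100 |

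**3. Power across the range, by the plan's formula.** Power = Φ(delta × √N / sigma − 1.96).

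- N = 16: Φ(2.667 − 1.96) = Φ(0.707) = 76.0%
- N = 18: Φ(2.828 − 1.96) = Φ(0.868) = 80.7%
- N = 30: 95.5%
- N = 50: 99.7%
- N = 100: above 99.99%

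Power is therefore at least 80% at every evaluable N of 18 or more. It falls short only if fewer than 18 are evaluable.

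**4. Precision.** The 95% half-width is t(0.975, N − 1) × 3 / √N. At N = 18 this is 2.110 × 0.707 = 1.49 RPM. At N = 100 it is 1.984 × 0.300 = 0.60 RPM. The ratio is about 2.5.

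**5. Error if enrolment stopped on the result.** This was simulated with 200,000 runs per scenario: true bias 2 RPM, SD 3 RPM, t-based two one-sided tests against ±2 RPM, stopping at the first pass. Section 8.1 uses z(alpha/2) = 1.96, so the 2.5% column is the one that matches the plan.

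| Looks at N = | False equivalence, 2.5% per side | 5% per side |
|---|---|---|
| 18 only | 2.5% | 4.9% |
| 18, 100 | 4.6% | 9.0% |
| 18, 50, 100 | 5.9% | 11.2% |
| 18, 28, …, 98, 100 | 8.9% | 15.6% |
| every subject, 18 to 100 | 12.1% | 20.4% |

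**The case against.** The best defence is that the sentence has a natural reading: 18 usable subjects as a floor and 100 as an administrative ceiling. The word used in section 5 is permissive, so the plan does not predict 82% loss. On that reading power meets its target throughout. This stands as far as power goes. A reader might infer that an open range leaves the stated 80% power attached to no design; the plan's own formula contradicts that. But the plan never says that the 18 are evaluable, and a generous ceiling still needs a reason and a rule for stopping below it.

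A reader might also infer that the sponsor means to stop at a favourable result. The documents do not support that. No look is scheduled. RRref requires manual annotation of the raw acoustic recordings (section 2.1, reference methods), and the bedside breath counts on the CRF are not that reference. A look after every subject is thus the least plausible scenario. Site staff recruit the subjects (section 6.4), and the data-ready step in section 11.4 can be read as a gate before analysis. All of this stands, and it makes the inflation an unguarded possibility and not a feature of the plan.

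Finally, section 8.2 contains no pass criterion, so the error rates belong to a test inferred from section 8.1. That also stands, and the figures are conditional on it.

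Sections 6.4 and 7.1.3 differ on when a subject counts as enrolled: at signed consent, or only after eligibility is confirmed. That is a clerical mismatch and does not carry this point.

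**Conclusion.** The point holds as a gap in specification. The 18-to-100 range is not derived from the reason given for it: any loss up to 50% needs at most 36 enrolled. The unit of the 18 is undefined, which matters by about 5 percentage points of power if 16 and not 18 are evaluable (76.0% against 80.7%). Expected precision is left open between half-widths of about 1.5 and 0.6 RPM.

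The effect on false equivalence is conditional: from 2.5% to about 6% with three looks, and at most about 12% with a look after every subject. It rests on three assumptions: that the equivalence test implied by section 8.1 is the decision rule, that the comparison is made while enrolment is open, and that enrolment ends at the first pass. The plan provides for none of these and rules out neither early comparison nor stopping on it. With the size fixed independently of the results, the error rate is not affected. The change is worth making because it closes this route for the price of a few sentences.

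**What to change.** In section 8.1, replace the range with:

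1. One fixed number of evaluable subjects, defined as those with valid paired RRa and RRref data.
2. An enrolment cap derived from a stated loss rate, for example 23 enrolled for 18 evaluable at 20% loss. If a size near 100 is intended, state it as the planned size and give its precision.
3. A statement that no RRa versus RRref comparison is computed until enrolment is closed.

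Use one definition of enrolment in sections 6.4 and 7.1.3, so that the cap has a clear unit.

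The cost is protocol wording, with no extra subjects if 18 evaluable is kept. The sponsor gives up the freedom to extend or stop enrolment after seeing results. Fixing the size at 18 also accepts the widest interval in the range, about 1.5 RPM against 0.6 at 100.

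Before fixing 18, settle one separate matter. The plan's formula counts the type II error against one limit only. For two one-sided tests at zero true bias with a 95% interval, the normal approximation at N = 18 gives 2 × 0.8074 − 1, about 61% power; 80% needs ((1.96 + 1.2816) × 3 / 2)² = 23.64, so 24 evaluable. If that test is to be the decision rule, the fixed number should be calculated for it.
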